#### 10.4.4.4. Follow-up of AEs and SAEs

The Investigator is obligated to perform or arrange for the conduct of supplemental measurements and/or evaluations as medically indicated, or as requested by Sponsor and/or Medical Monitor, to elucidate the nature and/or causality of the AE or SAE as fully as possible. This may include additional laboratory tests or investigations, histopathological examinations, or consultation with other health care professionals.

- If a participant dies during participation in the study or during a recognized follow-up period, the Investigator will provide the Sponsor with a copy of any postmortem findings including histopathology.
- New or updated information will be recorded in the originally completed eCRF.
- The Investigator will submit any updated SAE data to the SAE coordinator within 24 hours of receipt of the information.

#### 10.4.5. Reporting of SAEs

Facsimile or electronic transmission of the SAE Report Form is the preferred method to transmit this information to the SAE Submission Coordinator.

In rare circumstances and in the absence of facsimile equipment, notification by telephone is acceptable with a copy of the SAE data collection tool sent by overnight mail or courier service.

Initial notification via telephone does not replace the need for the Investigator to complete and sign the SAE Report Form within the designated reporting time frames.

Contacts for SAE reporting can be found on page 3.

## **10.5. Appendix 5: Contraceptive and Collection of Pregnancy Information**

### **10.5.1. Definitions**

#### **Woman of Childbearing Potential (WOCBP)**

A woman is considered fertile following menarche and until becoming post-menopausal unless permanently sterile (see below). If fertility is unclear (e.g., amenorrhea in adolescents or athletes) and a menstrual cycle cannot be confirmed before the first dose of study intervention, additional evaluation should be considered.

#### **Women in the following categories are not considered WOCBP**

1. Premenarchal
2. Premenopausal with one of the following:
  - Documented hysterectomy
  - Documented bilateral salpingectomy
  - Documented bilateral oophorectomy

For individuals with permanent infertility due to an alternate medical cause other than the above, (e.g., müllerian agenesis, androgen insensitivity), investigator discretion should be applied to determining study entry.

Note: Documentation can come from the site personnel's review of the participant's medical records, medical examination, or medical history interview.

3. Postmenopausal
  - A postmenopausal state is defined as no menses for 12 months without an alternative medical cause. A high follicle-stimulating hormone (FSH) level in the postmenopausal range may be used to confirm a postmenopausal state in women not using hormonal contraception or hormonal replacement therapy (HRT). However, in the absence of 12 months of amenorrhea, confirmation with more than one FSH measurement is required.
  - Female participants on HRT and whose menopausal status is in doubt will be required to use one of the non-estrogen hormonal highly effective contraception methods if they wish to continue their HRT during the study. Otherwise, they must discontinue HRT to allow confirmation of postmenopausal status before study enrollment.

### **10.5.2. Contraception Guidance**

#### **Male participants**

Male participants with female partners of childbearing potential are eligible to participate if they agree to ONE of the following from Day 1 through 12 weeks after the last dose of study intervention:

- Are abstinent from penile-vaginal intercourse as their usual and preferred lifestyle (abstinent on a long-term and persistent basis) and agree to remain abstinent
- Agree to use a male condom plus partner use of a contraceptive method with a failure rate of < 1% per year, as described in [Table 7](#), when having penile-vaginal intercourse with a WOCBP who is not currently pregnant

Male participants must refrain from donating sperm for the duration of the study and for 12 weeks after the last dose of study intervention.

Male participants with a pregnant or breastfeeding partner must agree to remain abstinent from penile-vaginal intercourse, or use a male condom during each episode of penile penetration during the protocol-defined time frame.

### **Female participants**

Female participants of childbearing potential are eligible to participate if they agree to use a highly effective method of contraception consistently and correctly throughout the study and for 12 weeks following the last dose of study intervention, as described in [Table 7](#).

**Table 7: Highly Effective Contraceptive Methods**

Highly Effective Contraceptive Methods That Are User Dependenta Failure rate of < 1% per year when used consistently and correctly.	

 
Combined (estrogen- and progestogen-containing) hormonal contraception associated with inhibition of ovulation               
 
– Oral
 
– Intravaginal
 
– Transdermal
 
 
 
	

 
Progestogen-only hormonal contraception associated with inhibition of ovulation               
 
– Oral
 
– Injectable
 
 
 
	
Highly Effective Methods That Are User Independenta	

 
Implantable progestogen-only hormonal contraception associated with inhibition of ovulation               
 
– Intrauterine device (IUD)
 
– Intrauterine hormone-releasing system (IUS)
 
– Bilateral tubal occlusion
 
 
 
	

 
Vasectomized partner A vasectomized partner is a highly effective contraception method, provided that the partner is the sole male sexual partner of the WOCBP and the absence of sperm has been confirmed. If not, an additional highly effective method of contraception should be used.
 
	

 
Sexual abstinence Sexual abstinence is considered a highly effective method only if defined as refraining from heterosexual intercourse during the entire period of risk associated with the study intervention. The reliability of sexual abstinence needs to be evaluated in relation to the duration of the study and the preferred and usual lifestyle of the participant.
 
	

a Typical-use failure rates may differ from those when used consistently and correctly. Use should be consistent with local regulations regarding the use of contraceptive methods for participants participating in clinical studies.

Note: In Japan, contraceptive drugs or devices used must be approved or certified in Japan.

**10.5.3. Pregnancy Testing**

- WOCBP should only be included after a confirmed menstrual period and a negative highly sensitive urine or serum pregnancy test. Positive urine tests should be confirmed with a serum test.
- Additional pregnancy testing should be performed at monthly intervals during the treatment period and as required locally.
- Pregnancy testing will be performed whenever a menstrual cycle is missed or when pregnancy is otherwise suspected.
- Pregnancy testing will be performed 2 to 3 weeks after administration of the last dose of study intervention in any WOCBP who prematurely discontinues the study.
- Pregnancy testing with a sensitivity of at least 10 mIU/mL will be performed.

**10.5.4. Collection of Pregnancy Information**

Male participants with partners who become pregnant

- The Investigator will attempt to collect pregnancy information on any male participant's female partner who becomes pregnant while the male participant is in this study.
- After obtaining the necessary signed informed consent from the pregnant female partner directly, the Investigator will record pregnancy information on the appropriate form and submit it to the Sponsor within 24 hours of learning of the partner's pregnancy. The female partner will also be followed to determine the outcome of the pregnancy. Information on the status of the mother and child will be forwarded to the Sponsor. Generally, the follow-up will be no longer than 6 to 8 weeks following the estimated delivery date. Any termination of the pregnancy will be reported regardless of fetal status (presence or absence of anomalies) or indication for the procedure.

Female Participants who become pregnant

- The Investigator will collect pregnancy information on any female participant who becomes pregnant while participating in this study. Information will be recorded on the appropriate form and submitted to the Sponsor within 24 hours of learning of a participant's pregnancy.
- The participant will be followed to determine the outcome of the pregnancy. The Investigator will collect follow-up information on the participant and the neonate and the information will be forwarded to the Sponsor. Generally, follow-up will not be required for longer than 6 to 8 weeks beyond the estimated delivery date. Any termination of pregnancy will be reported, regardless of fetal status (presence or absence of anomalies) or indication for the procedure.
- While pregnancy itself is not considered to be an AE or SAE, any pregnancy complication or elective termination of a pregnancy will be reported as an AE or SAE. A spontaneous abortion is always considered to be an SAE and will be reported as such. Any post-study pregnancy-related SAE considered reasonably related to the

study intervention by the Investigator will be reported to the Sponsor as described in Section 10.4.5. While the Investigator is not obligated to actively seek this information in former study participants, he or she may learn of an SAE through spontaneous reporting.

- Any female participant who becomes pregnant while participating in the study will discontinue study intervention.

## 10.6. Appendix 6: Liver Safety: Suggested Actions and Follow-up Assessments

All participants will be monitored for possible signs of DILI. Safety laboratories will be monitored by a central laboratory in real time with potential DILI alerts sent to the Investigator.

### PARTICIPANTS AGED $\geq 6$ YEARS OF AGE

For participants with normal liver biochemistries at baseline:

- **Close Monitoring:** An increase of serum ALT or AST to  $> 3 \times$  ULN should be followed by repeat testing of ALT, AST, alkaline phosphatase, and total bilirubin within 48 to 72 hours to confirm the abnormalities and to determine if they are increasing or decreasing. Inquiry should also be made about symptoms, strenuous exercise, or previous seizures. Repeat testing 2 or 3 times weekly is recommended. All participants showing possible DILI should be followed until abnormalities return to normal or to the baseline state. If a participant lives remote from the study site, local testing may be performed, and the test results reported to the Investigator (along with the reference ranges for the local laboratory).
- **Study Intervention Discontinuation:** Study intervention will be discontinued when a participant meets one of the conditions outlined below (from 2009 FDA Guidance for Industry-Drug Induced Liver Injury: Premarketing Clinical Evaluation) or if the Investigator believes that it is in best interest of the participant.
  - ALT or AST  $> 8 \times$  ULN
  - ALT or AST  $> 5 \times$  ULN for more than 2 weeks
  - ALT or AST  $> 3 \times$  ULN and (total bilirubin  $> 2 \times$  ULN or INR  $> 1.5$ )
  - ALT or AST  $> 3 \times$  ULN with the appearance of fatigue, nausea, vomiting, right upper quadrant pain or tenderness, fever, rash, and/or eosinophilia ( $> 5\%$ )

For participants with elevated transaminases at baseline:

The following Alternative DILI Monitoring Algorithm should be used.

- **Close Monitoring:** If participants develop elevations of AST or ALT  $> 2$  times baseline or total bilirubin  $> 1.5$  times baseline while on study, testing should be repeated within 48 to 72 hours. Persistent elevations should be followed by repeat testing and physical examination 2 to 3 times per week, with or without study intervention discontinuation (see below).
- **Study Intervention Discontinuation:** Study intervention will be discontinued for abnormal liver function when a participant meets the following condition:
  - ALT or AST  $> 5 \times$  baseline, with baseline  $< 2 \times$  ULN

Close monitoring should be continued. If a participant lives remote from the study site, local testing may be performed, and the test results reported to the Investigator (along with the reference ranges for the local laboratory).

Discontinuation from study intervention does not mean discontinuation from the study, and remaining study procedures should be completed as indicated by the SoA.

Participants should be monitored at each study visit and instructed to call the Investigator for new or worsening symptoms of clinical hepatitis. Both symptoms and calls should be captured in dedicated case report forms.

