**Diagnostic assessments**

9. Liver function test (LFT) abnormalities: ALT and/or AST >  $1.5 \times \text{ULN}$  for age and gender

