## **7. DISCONTINUATION OF STUDY INTERVENTION AND PARTICIPANT DISCONTINUATION/WITHDRAWAL**

### **7.1.1. Discontinuation of Study Intervention Stopping Rules for Individual Participants**

Study intervention for an individual participant may be permanently discontinued at any time at the discretion of the Investigator.

Study intervention for an individual participant will be permanently discontinued for any of the following:

- any SAE possibly, probably, or definitely related to study intervention; unless, before the next scheduled dose, the SAE is reconsidered to be not related to study intervention or has resolved AND continued drug treatment in the study is considered safe by the SRC.
- any of the changes in hepatic function detailed in Section 7.1.1.1.
- pregnancy, as detailed in Section 10.5.

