##### **5. Is a congenital anomaly/birth defect**

##### **6. Other situations**

Medical or scientific judgment should be exercised in deciding whether SAE reporting is appropriate in other situations such as important medical events that may not be immediately life-threatening or result in death or hospitalization but may jeopardize the participant or may require medical or surgical intervention to prevent one of the other outcomes listed in the above definition. These events should usually be considered serious.

Examples of such events include invasive or malignant cancers, intensive treatment in an emergency room or at home for allergic bronchospasm, blood dyscrasias or convulsions that do not result in hospitalization, or development of drug dependency or drug abuse.

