### **Study Intervention Interruption/Discontinuation**

**Study drug must be interrupted** if any of the following criteria are met (applies to participants with normal and elevated transaminases at baseline):

- ALT or AST  $> 8 \times$  ULN
- ALT or AST  $> 5 \times$  ULN for 2 weeks or longer
- ALT or AST  $> 3 \times$  ULN in association with total bilirubin  $> 2 \times$  ULN and/or clinical jaundice or other signs of liver dysfunction (hepatomegaly, pruritus, bleeding, etc).

As children can have LFT elevation from viral infections and medications, an investigation of potential alternative causes (acetaminophen use, EBV, CMV infection, etc) and physical examination should be conducted, and the participant should be closely monitored for clinical progression. **If no alternative etiology is identified, the participant should be discontinued from the study, even if the participant has a normal physical exam.**

If an alternative, reversible cause of transaminase elevation has been identified, and the physical examination is normal the medical monitor should be consulted, and study drug may be resumed after the investigator has confirmed the participant's clinical stability and the transaminases are back to  $< 2 \times$  ULN. Transaminases and bilirubin should be monitored at least weekly for 4 weeks after resuming study drug. **If a protocol defined transaminase elevation ( $> 3 \times$  ULN for participants with normal baseline or  $> 2 \times$  baseline for those**

**with elevated baseline) recurs after re-challenge with the study drug the study drug should be permanently discontinued, regardless of the etiology.**

If a participant lives remote from the study site, local testing may be performed, and the test results reported to the Investigator (along with the reference ranges for the local laboratory).

Participants should be monitored at each study visit and instructed to call the Investigator for new or worsening symptoms of clinical hepatitis and/or liver dysfunction. Both symptoms and calls should be captured in dedicated eCRFs.

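### Participants aged 6 and over with elevated baseline transaminases have no mandated liver stop for a combined ALT/bilirubin or ALT/INR rise, or for a prolonged rise, below 5 × baseline

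*Protocol*

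**What the plan says.** Protocol 10.6 sets liver rules by age and, from age 6, by baseline.

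- **Age 6 and over, normal liver biochemistries at baseline.** Drug is stopped for any one of four findings: ALT or AST above 8 × ULN; above 5 × ULN for more than 2 weeks; above 3 × ULN with bilirubin above 2 × ULN or INR above 1.5; or above 3 × ULN "with the appearance of fatigue, nausea, vomiting, right upper quadrant pain or tenderness, fever, rash, and/or eosinophilia" (above 5%).
- **Age 6 and over, elevated transaminases at baseline.** An alternative algorithm applies. ALT or AST above 2 × baseline, or bilirubin above 1.5 × baseline, leads to repeat testing. The stopping rule reads "Study intervention will be discontinued for abnormal liver function when a participant meets the following condition" and lists one item: ALT or AST above 5 × baseline, with baseline below 2 × ULN.
- **Under 6, any baseline.** Drug must be interrupted "if any of the following criteria are met (applies to participants with normal and elevated transaminases at baseline"). The criteria are ALT or AST above 8 × ULN; above 5 × ULN for 2 weeks or longer; and above 3 × ULN with bilirubin above 2 × ULN "and/or clinical jaundice or other signs of liver dysfunction (hepatomegaly, pruritus, bleeding, etc").

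Protocol 7.1.1 adds two provisions for everyone: investigator discretion, and a mandatory stop for "any SAE possibly, probably, or definitely related to study intervention", with an exception decided before the next dose.

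**The concern.** A transaminase rise together with a bilirubin or INR rise is the pattern that liver stopping rules chiefly exist to catch. In the older elevated-baseline group, bilirubin leads only to more testing, INR does not appear, and persistence leads to more frequent testing but not to a mandated stop. The under-6 section shows that the protocol regards ULN-based combined and duration thresholds as workable for children whose transaminases start high, so baseline adjustment alone does not explain their absence here. What is at stake is a further monthly dose of a liver-targeted siRNA that depends on judgement, where comparable children would be stopped or interrupted by rule.

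**Working it through.** **Inputs**
- Elevated-baseline stop: 5 × baseline, only if baseline is below 2 × ULN (Protocol 10.6).
- Comparator thresholds: 3 × ULN combined, 5 × ULN with duration, 8 × ULN single value (Protocol 10.6).
- Entry limit: exclusion criterion 9 (Protocol 5.2), "Liver function test (LFT) abnormalities: ALT and/or AST" above 1.5 × ULN. An elevated screening baseline *b* therefore lies above 1.0 and up to 1.5 × ULN.
- Group size: about 7 planned completers aged 6 to 11 (Protocol 1.1).

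**Formulas, all in multiples of ULN.** Existing stop = 5*b*. Width of the combined gap = 5*b* − 3. Width of the duration gap = 5*b* − 5. Start of close monitoring on ALT or AST = 2*b*.

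| Baseline *b* | Monitoring from 2*b* | Existing stop 5*b* | Combined gap 5*b* − 3 | Duration gap 5*b* − 5 |
|---|---|---|---|---|
| approaching 1.0 | 2.0 | 5.0 | 2.0 | 0 |
| 1.2 | 2.4 | 6.0 | 3.0 | 1.0 |
| 1.5 | 3.0 | 7.5 | 4.5 | 2.5 |

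The duration gap is the narrower one and runs from 5 to at most 7.5 × ULN. Monitoring starts at or below 3 × ULN in every row, so each case in the gap is already being retested. On a single ALT value this group is stopped earlier than normal-baseline children (at most 7.5 against 8).

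**Cases**
- *b* = 1.2, ALT 4 × ULN, bilirubin 3 × ULN. ALT is 4 / 1.2 = 3.3 × baseline, below 5, so no stop is mandated. A child of the same age with normal liver biochemistries must stop; a child under 6 must be interrupted.
- ALT 4.5 × ULN with INR 1.8. No stop is mandated, since the existing threshold is above 5.0 for every elevated baseline. A child aged 6 or over with normal liver biochemistries must stop.
- ALT 6 × ULN for 3 weeks. At *b* = 1.1 the stop is 5 × 1.1 = 5.5, so the child stops. At *b* = 1.25 it is 5 × 1.25 = 6.25, so the child does not.

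**Where an 8 × ULN line would matter.** It acts before 5*b* only if *b* > 8 / 5 = 1.6, above the entry limit. A higher baseline could arise if the Day 1 pre-dose sample served as the liver baseline. Appendix 6 does not define that baseline, and footnote g of the Schedule of Activities exempts laboratory tests from the Day 1 eligibility re-check. At *b* of 2 or more the single listed stop does not apply at all: *b* = 2 with ALT 15 × ULN and nothing else abnormal meets no listed stop.

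**Separate smaller point.** For an unexplained case under 6, Appendix 6 removes the child from the study. Protocol 7.1.1 and the older-age part of 10.6 keep a child on scheduled visits after a drug stop. Six monthly urine visits are planned after baseline (Days 30 to 180). Removal after visit *k* loses 6 − *k* of them, or 5 − *k* if the early termination visit is mapped forward under SAP 4.1.1.5. For a PH1 child these are data that the treatment-policy strategy in SAP 1.1.2 would use.

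**The case against.** The strongest reply is that these children are watched closely and can be stopped. Repeat testing is due within 48 to 72 hours and then 2 to 3 times a week if the rise persists. "Safety laboratories will be monitored by a central laboratory in real time with potential DILI alerts sent to the Investigator". Protocol 8 sends immediate safety concerns to the Sponsor to decide on continuation, and 2.3.4 provides medical monitor review. Dosing is monthly, so at most five dosing decisions follow Day 1. A combined rise could also be classed as an important medical event; Protocol 10.4.2 says of such events, "These events should usually be considered serious". If also judged at least possibly related, it triggers the mandatory stop in 7.1.1. All of this stands and shrinks the practical gap. But each route is monitoring or needs a judgement of seriousness, causality or safety; none is a laboratory threshold that mandates a stop.

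The reply is also right about the symptom criterion. At a baseline of 1.5 × ULN, 3 × ULN is 3 / 1.5 = 2.0 × baseline, so copying it would stop a child for a doubling of ALT with fever or vomiting. Appendix 6 itself notes that viral infections raise liver tests in children. That trade-off belongs to clinical safety.

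A reader might infer several stronger things that the documents do not support.
- *The rule sets contradict each other.* They cover separate groups, so this is an omission.
- *Every other child in the study would be stopped or interrupted.* A child aged 6 or over with normal transaminases but another abnormal liver test at baseline fits neither list on its face.
- *The wrong section number disables the hepatic stop.* Sections 7.1.1.1 to 7.1.1.3 do point to 10.5, which is contraception, but 10.6 carries its own mandatory wording.
- *Section 7 leaves no room for interruption and resumption.* 7.1.1.2 and 7.1.1.3 provide for both.

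**Conclusion.** The point holds as a low-frequency safety gap. In participants aged 6 and over with elevated baseline transaminases, no stop is mandated for a combined rise between 3 × ULN and 5 × baseline (upper end above 5.0 and up to 7.5 × ULN), or for a prolonged rise between 5 × ULN and that same level. The width rests on the screening limit of 1.5 × ULN governing the baseline. The number affected is unknown: the documents give no share with elevated baseline, known causes of transaminase elevation are excluded (criterion 5b), and the group may be empty. The reason to act is the severity of a combined rise and the ease of the change, not expected frequency. The under-6 removal wording is a real but separate inconsistency, and its effect on the primary estimand is confined to PH1. The section-number slip is editorial.

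**What to change.** In the next amendment or a safety clarification letter:

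1. Add three criteria to the list for age 6 and over with elevated baseline: ALT or AST above 3 × ULN with either total bilirubin above 2 × ULN or INR above 1.5; ALT or AST above 5 × ULN lasting more than 2 weeks; and ALT or AST above 8 × ULN. Keep the 5 × baseline stop. The 8 × ULN line changes nothing at entry-eligible baselines; it acts above 1.6 × ULN and gives a baseline of 2 × ULN or more a single-value stop.
2. Ask clinical safety whether the symptom criterion should also apply, and in what form.
3. Separately, in the under-6 text, replace removal from the study with permanent discontinuation of study intervention, and keep the child on the scheduled visits.
4. Editorially, change 10.5 to 10.6 in 7.1.1.1, 7.1.1.2 and 7.1.1.3.

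The cost is wording plus an occasional extra drug stop. That stop would be permanent under 7.1.1. Although 7.1.1.3 allows rechallenge, 10.6 gives no resumption criteria for this age group, so the clinical safety review could consider whether to add some.
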